6.3 Micro-RNA analysis

As mentioned previously, higher levels of miR-29b were associated with clinical response. We will evaluate this prospectively by analyzing pre-treatment bone marrow samples for the relevant micro-RNAs in collaboration with the laboratory of [name].

6.4 Assessment of immune function and effector cells

The role of an intact immune effector cell function towards response and eradication of minimal residual disease will be evaluated in collaboration with [name] laboratory. Immune suppression is an unavoidable consequence of current therapeutic modalities and is associated with significant morbidity and mortality due to opportunistic infections. We have developed sensitive laboratory methods that allow the study of immune subset recovery (T cell, B cell and NK cell recovery). At this time, careful studies of immune recovery are not routinely performed in subjects with AML undergoing treatment with decitabine. Such studies would allow us to better understand the effects of the drug on the recovery of immune function in AML⁵⁰⁻⁵³.

We propose to systematically collect specimens of blood, bone marrow and plasma from patients with AML undergoing therapy with decitabine. Samples may be collected prior to initiation of therapy, at the time of achieving complete remission and suspected relapse and prior to every 3rd or 4th cycle of therapy; Omissions will not be considered as violations. Assays to be performed may include the following: 1) T cell immunophenotyping (to define the recovery of T cell subsets associated with a "naïve" or "memory" T cell phenotype); 2) Functional studies of antigen-specific T cell responses to pathogens and to leukemia-associated antigens (e.g., to defined epitopes that have been identified as potential malignancy-specific targets);^{1,2,3} 3) Studies examining the molecular diversity of the T cell repertoire;⁵ 4) Assays of plasma levels of cytokines (e.g., interleukin-7) that may be important in T cell reconstitution; 5) Studies to assess the role of other immune subsets involved in anti-pathogen and anti-leukemia responses including natural killer (NK) cells, B lymphocytes, antigen presenting cells (e.g. dendritic cell subsets) and subsets involved in immunoregulatory pathways such as macrophages and myeloid derived suppressor cells; 6) Molecular studies will be performed on total RNA or DNA extracted from PBMC to assess the role of immune-related genes in treatment outcome (infection and relapse). Some or all of these studies may be performed at the time of collection. In most cases, cryopreserved PBMC or plasma samples will be used for these assays. Cryopreserved cells in excess of requirements for studies of immune reconstitution will be banked to allow access of other investigators to these specimens.

7.0 Pre-study evaluations (to be performed within 14 days unless otherwise noted)

- 7.1 History and physical exam.
- 7.2 CBC, platelet count, differential; creatinine, bilirubin, SGPT (within 7 days).
- 7.3 Bone marrow aspirate (within 14 days) and cytogenetics
- **7.4** Molecular studies in bone marrow specimens for FLT3-ITD, FLT3-TKD, NPM1, IDH1, IDH2, DNMT3A, TET2, EZH2, RAS, JAK2 (if appropriate, e.g. in patients

with history of MPN), and the Leukemia mutation panel (whichever is available at the time of enrollment)

- 7.5 Whole genome sequencing (performed at [name] laboratory)
- **7.6** Blood sample (20-50 cc) and marrow aspirate sample (2 cc) for methylation studies, to be sent to [name] laboratory. Not all samples may be collected at all times points and omissions will not be considered deviations. Samples obtained prior to consenting may be used.
- **7.7** Blood sample (25-35cc) will be collected for assessment of immune function and effector cells to be sent to [name] lab. Not all samples may be collected at all times points and omissions will not be considered deviations. Samples obtained prior to consenting may be used.
- **7.8** Pregnancy (urine or blood) test only for women of childbearing potential within 7 days.

8.0 Evaluations during the study

- **8.1** CBC, differential, platelet count 1-2 times weekly for 1st course, then every 2-4 weeks while on therapy. The frequency can be reduced to once per cycle after achieving CR or after sixth cycle (whichever first)
- **8.2** Creatinine, bilirubin, SGPT weekly for 1st course, then every 2-4 weeks while on therapy. The frequency can be reduced to once per cycle after achieving CR or after sixth cycle (whichever first)
- **8.3** Bone marrow aspiration to document remission then every 1-3 courses.
- **8.4** Cytogenetics at remission if abnormal pretherapy any time a bone marrow exam is performed. Omissions will not be considered as deviations.
- **8.5** Molecular testing depending on the positive tests pre-study (specific mutations, whole genome sequencing) any time a bone marrow exam is performed. Omissions will not be considered as deviations.
- **8.6** Multi-parameter flow cytometry for the presence of leukemia associated immunophenotype (minimal residual disease) any time a bone marrow exam is performed. Omissions will not be considered as deviations..
- 8.7 Blood samples (20-50cc) on days 1 (any time prior to first dose), 5 and 10 (+/- 3 days) of therapy (optional); marrow sample (2 cc) every 1-3 courses (optional). Samples are to be sent to [name] lab ([contact]). (Not all research samples may be collected at all time-points and omissions will not

be considered deviations.) Precourse samples may be obtained after day 27 of the preceding course, but prior to first dose of next course.

- **8.8** Blood sample (25-35cc) will be collected for assessment of immune function and effector cells at the time of remission, relapse, and about every 3 4 cycles. Samples are to be sent to [name] lab. (Not all samples may be collected at all times points and omissions will not be considered deviations.)
- **8.9** Peripheral blood specimens will be obtained at the time of complete remission and relapse, and evaluated for the presence of various T-cell subsets, NK cells and other immune effector measures

9.0 Response criteria

- **9.1** Complete Remission: Normalization of the peripheral blood and bone marrow with $\leq 5\%$ bone marrow blasts, a peripheral blood granulocyte count $\geq (1.0 \times 10^9/L)$, and a platelet count $\geq 100 \times 10^9/L$).
- **9.2** Partial Remission: as above except for the presence of 6-15% marrow blasts, or 50% reduction if <15% at start of treatment.
- **9.3** Complete remission with incomplete recovery (CRi): meets all criteria for CR except for platelet recovery to $\geq 100 \times 10^9$ /L and/or granulocyte count $\geq (1.0 \times 10^9)$ /L
- **9.4** Clinical benefit: platelets increase by 50% and to above 30×10^9 /L untransfused (if lower than that pretherapy); or granulocytes increase by 100% and to above 10^9 /L (if lower than that pretherapy); or hemoglobin increase by 2 g/dl; or transfusion independent; or splenomegaly reduction by $\ge 50\%$; or monocytosis reduction by $\ge 50\%$ if pretreatment $> 5 \times 10^9$ /L.

10.0 Criteria for removal from the study

- **10.1** No improvement or clinically significant progressive disease
- **10.2** Patient refusal
- **10.3** Pattern of patient non-compliance; physician judgment

11.0 Statistical Considerations

11.1 General description

This is a Phase II open-label, efficacy and toxicity study of two treatment arms (arm A: Decitabine 20mg/m^2 IV daily for 5 days versus arm B: Decitabine 20mg/m^2 IV daily for 10 days) in subjects with AML ≥ 60 or unfit for standard cytotoxic chemotherapy. Patients will be enrolled to evaluate the 2 dose schedules. For both arms, one course will consist of 4 weeks. An adaptive randomization design will be employed to compare the efficacy between the two arms. The primary efficacy outcome is the complete response which is defined as the complete remission (CR) or complete remission with incomplete recovery (CRi) assessed after three cycles. At the end of the trial, we will estimate the probability that one arm is superior to the other. We will also evaluate toxicity on each arm. A maximum of 100 patients will be accrued, at an expected accrual rate of 5 patients per month.

11.2 Randomization

The Department of Biostatistics will provide and maintain a website ("Clinical Trial Conduct": https://biostatistics.mdanderson.org/ClinicalTrialConduct/) for patients enrolled on this study. The Clinical Trial Conduct website resides on a secure server, and access is gained through usernames and passwords provided to personnel responsible for enrolling patients and updating patient data. The website is accessed through a browser using secure socket layer (SSL) technology. Personnel responsible for enrolling patients on trials, which includes the principal investigator(s), research nurse(s), and data coordinator(s), will be trained by members of the Department of Biostatistics (specifically the statistical collaborators on the study) in the use of the trial website; the importance of timely updating of follow-up times and recording of events will be emphasized in training.

11.3 Study Design

A maximum of 100 patients will be adaptively randomized into two treatment groups:

Arm A: Decitabine 20mg/m2 IV daily for 5 days

Arm B: Decitabine 20mg/m2 IV daily for 10 days

Patients will be assigned to receive different schedules of Decitabine, using an adaptive procedure that bases assignment probabilities on observed results in preceding patients. At first, 20 patients will be assigned to each arm with equal probability. As efficacy data accrues, patient assignment to the two arms will become unbalanced in favor of the one that has the higher complete response rate (RR). The RR for both arms will be estimated with a 95% CI (similar to Bayesian highest posterior density interval).⁴⁹

Based on previous studies, we expect a RR of about 30% in both arms. Therefore, we assume RR has a prior Beta distribution (0.6, 1.4) with mean 0.3. Let RRa and RRb denote the response rates for arm A and arm B, respectively. Beginning with the 21st patient in each arm and for each subsequent patient, we will compare RRa with RRb, incorporating data from all patients with evaluable response. In order to avoid favoring one arm earlier in a large trial, instead of assigning patients with posterior probability (Pa=Pr(RRa>RRb|data) and Pb=1-Pa), we use the following formula to assign patients:

2012-1017 May 24, 2017 Page **23** of **29**

Aa= $\frac{\sqrt{Pa}}{\sqrt{Pa} + \sqrt{Pb}}$, Ab=1-Aa, where Aa is the probability of assigning patients to arm A, Ab is the

probability of assigning patients to arm B, Pa is the posterior probability that arm A is superior to arm B and Pb is the posterior probability that arm B is superior to arm A.

If at any point during the trial Pr(RRa>RRb|data)>0.95(or <0.05) the schedule A(or B) will be selected as superior. If accruing information gives strong evidence that a RR of 30% or greater is unlikely to be true for any one of the treatment arms (Pr(RRa or RRb>0.3|data)<0.05), assignment to that arm will be stopped. If the maximum of 100 patients is enrolled and evaluated and Pr(RRa>RRb|data)>0.9 (or <0.1), we will declare that arm A(or B) has a higher RR rate than arm B (or A). Otherwise, the trial will be inconclusive. We used simulation (5,000 simulations per scenario) to evaluate the performance of the adaptive randomization procedure under several different scenarios (Table 2). Adaptive Randomization version 4.1 has been used for the simulation. Adaptive Randomization version 4.1 has been used for the simulation.

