5.2 Therapy

The initial Decitabine courses should be given at MD Anderson Cancer Center (or Regional Cancer Centers), either as in-patient or as out-patient. Decitabine will be dosed based on actual body weight. However, at the treating physician's discretion an adjusted body weight may be used, if actual body weight is >40% over ideal body weight. Adjusted body weight = ((Actual body weight – Ideal body weight) 0.4) + Ideal body weight. Decitabine may be subsequently administered at any of the Regional Cancer Centers (RCC) or at the patients' local oncologist offices. Patients will be assigned in a selective Bayesian design to one of two treatment arms.

- 1) Decitabine 20 mg/m² IV over approximately 1 hour daily x 5.
- 2) Decitabine 20 mg/m² IV over approximately 1 hour daily x 10.

Start at dose level 0 as shown below. There will be no dose escalation of Decitabine.

Patients will receive one course every 4-8 weeks; however delays of more than 8 weeks may be allowed if determined by the investigator to be in the best interest of the patient after discussion with the PI and the discussion documented in the patient's medical record. Doses may be given as close as 8 hours apart if approved by the PI. If prolonged aplasia and/or a major infection is seen, may decrease 1 dose level after marrow regeneration. This will be rounded to the following daily lower dose (15, 10, 7.5, 5 mg/m²). Otherwise continue at the same dose level every 4-8 weeks depending on recovery of counts and disease status. If persistent disease, start next course regardless of counts. If marrow complete response is achieved with adequate cellularity, start subsequent courses when granulocytes $\geq 0.75 \times 10^9$ /L and platelets $\geq 50 \times 10^9$ /L.

Patients on the 10 day regimen will receive 5 day dosing after achieving CR during consolidation/maintenance. The 5 day dosing may also be initiated in these patients after the first course, if it is thought to be in the best interest of the patient after discussion with the PI and the discussion documented in the patient's medical record. Patients on the 5 day regimen will continue to receive the 5 day regimen after the first course whether in CR or not.

Modifications of dose schedule or dose level other than above are allowed if felt to be in the patients best interest to optimize response or reduce toxicity. These decisions should be documented in the patient's medical record.

	Decitabine mg/m ²	² daily x days

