11.4 Toxicity Monitoring

Evidence of Toxicity will be monitored closely in all patients. For each arm, treatment will be terminated if Pr(non hematological grade 3 or higher clinically significant study drug related Toxicity >0.3 | data) >0.95. We assume $P_E \sim$ beta (0.3, 0.7). Table 1 shows the simulation of the trial. The treatment will be stopped accrual if the number of patients with clinically significant study drug related toxicities equal to or greater than indicated (i.e., #pts with tox) among the number of patients accrued (i.e., #pts): 2/2, 3/3, 4/5, 5/7, 6/9, 7/11, 8/14, 9/16, 10/19, 11/21, 12/24, 13/27, 14/29, 15/32, 16/35, 17/38, 18/40, 19/43, 20/46, 21/49, 22/52, 23/54, 24/57, 25/60, 26/63, 27/66, 28/69, 29/72, 30/75, 31/77. Multc99 version2.1 has been used for the simulation and boundary computation.

Table 1: OperaSafety Monitorsimulations)		
True	Stop	median
probability	probability	sample size (interquantile)
0.2	0.06	80 (80, 80)
0.25	0.13	80 (80, 80)
0.3	0.28	80 (45, 80)
0.35	0.53	65 (12, 80)

Table 2: Operating characteristics of adaptiverandomization design to compare DAC in twoschedules. Randomly assign 20 patients to eacharm with equal probability before adapting therandomization

	Arm A	Arm B
RR Rate	0.05	0.1
Expected # of Patients	20.1	20.1
Pr(Select)	0.02	0.14
Pr(Select Early)	0.01	0.10
Pr(Stop Early)	0.95	0.73
RR Rate	0.1	0.3
Expected # of Patients	21.5	22.6
Pr(Select)	0.003	0.66
Pr(Select Early)	0.001	0.52
Pr(Stop Early)	0.96	0.07
RR Rate	0.3	0.65
Expected # of Patients	21.7	24
Pr(Select)	0.0002	0.99
Pr(Select Early)	0.0002	0.98
Pr(Stop Early)	0.98	0.0002
RR Rate	0.3	0.3
Expected # of Patients	40.2	40.3
Pr(Select)	0.15	0.15
Pr(Select Early)	0.11	0.12
Pr(Stop Early)	0.21	0.2
RR Rate	0.5	0.6
Expected # of Patients	36.7	43
Pr(Select)	0.03	0.47
Pr(Select Early)	0.03	0.42
Pr(Stop Early)	0.42	0.03

2012-1017 May 24, 2017 Page **25** of **29**

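### Table 2 does not follow from the rules written in section 11.3: its 0.1/0.3 row implies at least 47.8 patients on average, on the natural reading of its labels, but prints 44.1

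*Combined protocol and SAP*

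**What the plan says.** The design rules are in section 11.3; Table 2, which reports their simulated performance, is printed under section 11.4.

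- Size and run-in: "A maximum of 100 patients will be adaptively randomized into two treatment groups", and "At first, 20 patients will be assigned to each arm with equal probability". The caption of Table 2 repeats the 20-per-arm run-in.
- Start of comparison: "Beginning with the 21st patient in each arm and for each subsequent patient, we will compare RRa with RRb".
- Early selection: "If at any point during the trial Pr(RRa>RRb|data)>0.95(or <0.05) the schedule A(or B) will be selected as superior".
- Futility and final selection: an arm whose posterior probability of a response rate above 0.3 falls below 0.05 is closed, and the text then turns to the end of the trial: "assignment to that arm will be stopped. If the maximum of 100 patients is enrolled and evaluated". The 0.9/0.1 cutoff belongs to that last condition. Otherwise the result is inconclusive.

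Section 11.3 gives closing an arm no other consequence. It does not end the trial at that point, and it does not allow the 0.9/0.1 cutoff before 100 patients.

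Table 2 reports, for each arm, the expected number of patients, Pr(Select), Pr(Select Early) and Pr(Stop Early). The documents do not define these labels.

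**The concern.** Table 2 is the only statement of the efficacy design's selection probabilities and expected size. Its figures should be what a team obtains by following section 11.3. In two rows the printed probabilities and the printed patient numbers cannot both be true under those rules, so at least one rule behind the simulation differs from the text or is missing from it.

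The gap lies in a decision the trial may well face: once one schedule is closed for futility, does the other keep enrolling, possibly to 100, or does the trial end and a winner get declared? The answer changes the expected size. It also changes the chance of declaring one schedule better when both have a 30% response rate, which is the rate section 11.3 expects in both arms.

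**Working it through.** **Inputs.** Section 11.3: run-in of 20 per arm (40 in total), maximum 100, Beta(0.6, 1.4) priors, square-root allocation, and the cutoffs above. Table 2: the printed rows. Arm A is the 5-day and arm B the 10-day schedule.

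**Printed totals.** At 0.1/0.3: 21.5 + 22.6 = 44.1 (at most 21.55 + 22.65 = 44.2 before rounding). At 0.05/0.1: 20.1 + 20.1 = 40.2 (at most 40.3).

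**Bound 1: late selection.** Read Pr(Select) minus Pr(Select Early) as selection that was not early. Under 11.3 such a trial has 100 patients, and every other trial has at least 40. Hence

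E[N] ≥ 40 + 60 × [Pr(Select B) − Pr(Select Early B)].

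| True A/B | Late selection of B | Bound as printed | Bound, worst-case rounding | Table 2 |
|---|---|---|---|---|
| 0.1/0.3 | 0.66 − 0.52 = 0.14 | 48.4 | 40 + 60 × (0.655 − 0.525) = 47.8 | 44.1 |
| 0.05/0.1 | 0.14 − 0.10 = 0.04 | 42.4 | 40 + 60 × (0.135 − 0.105) = 41.8 | 40.2 |

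The inequality holds within any set of simulated trials that share the rules, so simulation error cannot explain the shortfall. It does not depend on response delay. The other three rows do not violate it.

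**Bound 2: B still open.** If Pr(Stop Early) counts every stop of B, trials with no early selection and B not stopped must run to 100 under 11.3.

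- 0.1/0.3: 1 − 0.52 − 0.07 − 0.001 = 0.409, so E[N] ≥ 40 + 60 × 0.409 = 64.5 (63.9 after rounding), against 44.1.
- 0.05/0.1: 1 − 0.10 − 0.73 − 0.01 = 0.16, so E[N] ≥ 49.6 (48.7 after rounding), against 40.2.

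These are tests of consistency between Table 2's probabilities and the text. They do not estimate the size of the written design.

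**Simulation.** Checks start once 20 per arm are in, and responses are immediate. The column for the text as written lets the other arm continue after a drop. The last column ends the trial at the first drop and then applies 0.9/0.1 to the surviving arm. Most entries rest on 5,000 to 10,000 trials per row. In the last column, the 0.05/0.1 patient number rests on 3,000 and rows 0.3/0.65 and 0.5/0.6 on 1,500.

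| True A/B | Quantity | Table 2 | Text as written | Ends at first drop |
|---|---|---|---|---|
| 0.05/0.1 | N | 40.2 | 40.9–41.0 | 40.1 |
| | Select B | 0.14 | 0.141–0.145 (all early) | 0.163–0.172 |
| | Select B early | 0.10 | 0.141–0.145 | 0.132–0.135 |
| 0.1/0.3 | N | 44.1 | 50.8–51.6 | 43.7 |
| | Select B | 0.66 | 0.79 | 0.665–0.669 |
| 0.3/0.3 | N | 80.5 | 84.2–84.5 | 80.3–80.9 |
| | Select either | 0.15 + 0.15 = 0.30 | 0.37 | 0.296–0.313 |
| 0.3/0.65 | N | 45.7 | 44.6 | 45.2 |
| | Select B | 0.99 | 0.99 | 0.99 |
| 0.5/0.6 | N | 79.7 | 79.0 | 78.4 |
| | Select B | 0.47 | 0.48 | 0.49 |

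The text as written misses rows 0.1/0.3 and 0.3/0.3. It also misses the early-selection and stopping figures at 0.05/0.1, where B stops in 0.86 of trials against 0.73 printed. Ending at the first drop comes close in most rows but not at 0.05/0.1. There, early selection of B is 0.132 or more against 0.10, while the table's simulation error is about √(0.10 × 0.90 / 5,000) = 0.004.

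**Earlier monitoring.** Reading the early rule as active from the first patient gives about 28 patients at 0.1/0.3 and 16 at 0.05/0.1, so that reading does not reproduce the table either.

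**Response delay (assumption).** Response is "complete remission with incomplete recovery (CRi) assessed after three cycles", and section 5.2 says "Patients will receive one course every 4-8 weeks; however delays of more than 8 weeks may be allowed". Three courses at 4 to 8 weeks take 12 to 24 weeks. At 5 patients a month, about 5 × 12 × 12/52 = 14 to 5 × 12 × 24/52 = 28 patients are pending. Under the literal text at 0.3/0.3 (3,000 trials), 14 pending gives a total selection probability of 0.41 if checks start at 40 enrolled, or 0.35 at 40 evaluated. With 28 pending the figures are 0.47 and 0.34. N ranges from 78 to 94.

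**The case against.** The strongest reply is that Table 2 is sound and section 11.3 merely omits a sentence. With two arms, once one closes there is nothing left to randomize, so ending the trial there is a natural choice, and 11.3 never says the other arm carries on alone to 100. Simulating that choice comes near most rows, and the false-selection rate stays at about 0.30. On this view, 0.37 belongs to one reading of the text. Bound 1 also depends on labels the documents do not define, and the rows that fail it have an arm well below the expected 30%. Rows 0.3/0.65 and 0.5/0.6 barely move, and the cap of 100 is unaffected. Assignment is run through the biostatistics department's website (section 11.2), so staff are unlikely to apply 11.3 by hand.

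Much of this is fair. An unstated stopping and selection rule is a plausible cause, the 0.37 is conditional, and the label reading is an assumption. But no section supplies the missing rule. Ending at the first drop would not suffice by itself: the 0.9/0.1 cutoff would also have to apply before 100 patients, and 11.3 ties it to full enrolment and evaluation. Even with both changes the 0.05/0.1 row is not reproduced. The reply therefore gives a reason to amend the text and check the table, and it does not show that they agree. Section 11.2 does not state the drop rule either.

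**Conclusion.** The concern holds and should be fixed. Taking Pr(Select) minus Pr(Select Early) as late selection and 40 patients as the floor, the 0.1/0.3 row falls short of its minimum by at least 47.8 − 44.2 = 3.6 patients, after all rounding is taken in the table's favour. The 0.05/0.1 row also fails, by a smaller margin (41.8 − 40.3 = 1.5).

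With immediate responses and the other arm continuing, the written rules give about 51 patients and 0.79 selection of B at 0.1/0.3, and a false-selection rate of about 0.37 at 0.3/0.3 against 0.30 tabulated. Those figures depend on that reading. The inconsistency between text and table rests only on the label reading and the 20-per-arm run-in. Which rules the software actually used is not established.

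**What to change.** Reconcile section 11.3 with Table 2. State in 11.3:

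1. whether the trial ends or the other arm continues when one arm is dropped;
2. which cutoff then selects a schedule, and when it is applied;
3. that the superiority and futility checks start with the comparison at the 21st patient in each arm, and whether that counts enrolled or evaluated patients.

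Define the row labels of Table 2. Then re-run or confirm every row under the final rules and replace expected numbers, Pr(Select), Pr(Select Early) and Pr(Stop Early) with that output, not with the figures in this review. Adding sentences to 11.3 while leaving the table unchecked would not be enough, because no rule set tried here reproduces every row. If the re-run includes response delay, show a range of about 14 to 28 pending patients.

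The cost is a few sentences and one re-run of an existing simulation. If the literal text is kept, the stated chance of selecting a schedule when both are at 30% rises from 0.30 to about 0.37 with immediate responses.
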